### 12.6.2 Secondary Analyses

The analysis of COHb, MHBMA, 3-HPMA, and S-PMA at Day 90 and Total NNAL at Day 5 will be repeated for the PP Set.

The analysis of the COHb, MHBMA, 3-HPMA, S-PMA at Day 5/ Day 90 and Total NNAL at Day 90 will be repeated for the FAS as described in Section 12.6.1.1 "Analysis of Biomarkers of Exposure for Primary Endpoints". These endpoints will also be examined to compare the reductions in THS 2.2 Menthol vs. SA using the same methodology as for the primary analysis for the PP Set.

The baseline is for the biomarkers measured in urine is as defined in Section 12.1.4 "Definitions for Statistical Data Analysis".

#### 12.6.2.1 Analysis of Biomarkers of Exposure for Secondary Endpoints

The BoExp for the secondary endpoints are exhaled CO and total 1-OHP, Total NNN, 4-ABP, 1-NA, 2-NA, o-tol, CEMA, HEMA, B[a]P, HMPMA, S-BMA, Total NNAL and NEQ (all analysed from a 24-hour urine collection) at Day 5 and Day 90 will be described as reported in Section 12.1.3 "Descriptive Statistics". Urine parameters will be analyzed as concentrations adjusted for creatinine and the quantity excreted in urine over 24 hours. In addition the quantity excreted in urine over 24 hours for MHBMA, 3-HPMA, S-PMA and Total NNAL will also be presented as above.

All BoExp apart from CO breath test will be analyzed in the log scale.

BoExp will be analyzed using the same model described in Section 12.6.1.1 "Analysis of Biomarkers of Exposure for Primary Endpoints". No adjustment will be made for multiple comparisons. For all BoExp, if the results from the Day 5 analysis are significant (one-sided p-value  $\leq 0.025$ ) then the statistical significance will be evaluated for the results of the analysis at Day 90 values. LS means for each product along with the ratio (THS 2.2 Menthol : mCC) and 95% CI will be presented in the tables. Forest plots of the ratios and 95% CI will also be produced.

BoExp will also be examined to compare the reductions in THS 2.2 Menthol vs. SA using the same methodology as above for the PP Set. In addition, the sensitivity analyses described in Section 12.6.1.3 "Sensitivity Analysis" for the biomarkers of exposure for primary objectives will be repeated for the biomarkers of exposure for secondary objectives.

The data will be presented in the below outputs:

TFL number	Title
FIGURES	
15.1.1.2	Biomarkers of Exposure Geometric Mean and 95% CI – PP Set
15.1.1.4	Biomarkers of Exposure Geometric Mean and 95% CI – FAS
TABLES	
15.2.3.2	Analysis of COHb, MHBMA, 3-HPMA, S-PMA, and Total NNAL on Day 5/90 Visit versus mCC and SA for the Secondary Objective – PP Set.
15.2.3.3	Analysis of COHb, MHBMA, 3-HPMA, S-PMA, and Total NNAL on Day 5/90 Visit versus mCC and SA for the Secondary Objective – FAS.
15.2.3.4	Analysis of Additional Biomarkers of Exposure versus mCC and SA on Day 5/90 Visit – PP Set.
15.2.3.5	Analysis of Additional Biomarkers of Exposure versus mCC and SA on Day 5/90 Visit – FAS.
15.2.3.6	Sensitivity Analysis of Additional Biomarkers of Exposure versus mCC and SA using Mixed Model on Day 5/90 Visit – PP Set
15.2.3.7	Sensitivity Analysis of Additional Biomarkers of Exposure versus mCC and SA on Day 5/90 Visit – Compliant Population
15.2.4.1.2	Descriptive Statistics of Blood COHb (%) – FAS
15.2.4.1.3	Descriptive Statistics of Blood COHb (%) – Compliant Population
15.2.4.2.2	Descriptive Statistics of MHBMA in 24-hour Urine Collection – FAS
15.2.4.2.3	Descriptive Statistics of MHBMA in 24-hour Urine Collection – Compliant Population

TFL number	Title
15.2.4.3.2	Descriptive Statistics of 3-HPMA in 24-hour Urine Collection – FAS
15.2.4.3.3	Descriptive Statistics of 3-HPMA in 24-hour Urine Collection – Compliant Population
15.2.4.4.2	Descriptive Statistics of S-PMA in 24-hour Urine Collection – FAS
15.2.4.4.3	Descriptive Statistics of S-PMA in 24-hour Urine Collection – Compliant Population
15.2.4.5.2	Descriptive Statistics of Total NNAL in 24-hour Urine Collection – FAS
15.2.4.5.3	Descriptive Statistics of Total NNAL in 24-hour Urine Collection – Compliant Population
15.2.4.6.1	Descriptive Statistics of Exhaled CO (ppm) – PP Set
15.2.4.6.2	Descriptive Statistics of Exhaled CO (ppm) – FAS
15.2.4.7.1	Descriptive Statistics of 1-OHP in 24-hour Urine Collection – PP Set
15.2.4.7.2	Descriptive Statistics of 1-OHP in 24-hour Urine Collection – FAS
15.2.4.8.1	Descriptive Statistics of Total NNN in 24-hour Urine Collection – PP Set
15.2.4.8.2	Descriptive Statistics of Total NNN in 24-hour Urine Collection – FAS
15.2.4.9.1	Descriptive Statistics of 4-ABP in 24-hour Urine Collection – PP Set
15.2.4.9.2	Descriptive Statistics of 4-ABP in 24-hour Urine Collection – FAS
15.2.4.10.1	Descriptive Statistics of 1-NA in 24-hour Urine Collection – PP Set
15.2.4.10.2	Descriptive Statistics of 1-NA in 24-hour Urine Collection – FAS
15.2.4.11.1	Descriptive Statistics of 2-NA in 24-hour Urine Collection – PP Set
15.2.4.11.2	Descriptive Statistics of 2-NA in 24-hour Urine Collection – FAS
15.2.4.12.1	Descriptive Statistics of o-tol in 24-hour Urine Collection – PP Set
15.2.4.12.2	Descriptive Statistics of o-tol in 24-hour Urine Collection – FAS
15.2.4.13.1	Descriptive Statistics of CEMA in 24-hour Urine Collection – PP Set
15.2.4.13.2	Descriptive Statistics of CEMA in 24-hour Urine Collection – FAS
15.2.4.14.1	Descriptive Statistics of HEMA in 24-hour Urine Collection – PP Set

TFL number	Title
15.2.4.14.2	Descriptive Statistics of HEMA in 24-hour Urine Collection – FAS
15.2.4.15.1	Descriptive Statistics of B[a]P in 24-hour Urine Collection – PP Set
15.2.4.15.2	Descriptive Statistics of B[a]P in 24-hour Urine Collection – FAS
15.2.4.16.1	Descriptive Statistics of HMPMA in 24-hour Urine Collection – PP Set
15.2.4.16.2	Descriptive Statistics of HMPMA in 24-hour Urine Collection – FAS
15.2.4.17.1	Descriptive Statistics of S-BMA in 24-hour Urine Collection – PP Set
15.2.4.17.2	Descriptive Statistics of S-BMA in 24-hour Urine Collection – FAS
15.2.4.18.1	Descriptive Statistics of NEQ in 24-hour Urine Collection – PP Set
15.2.4.18.2	Descriptive Statistics of NEQ in 24-hour Urine Collection – FAS
LISTINGS	
15.3.3.1	Listing of Urinary Biomarkers
15.3.3.2	Listing of Bood, Plasma, Serum, and Exhaled Air Biomarkers

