2.1.2 Description of the Product and Scientific Findings

Thousands of chemicals - “smoke constituents” - are formed when tobacco is burned or combusted. More than 5,300 smoke constituents have been identified (Rodgman and Perfetti, 2009), and more than 100 of them have been categorized as harmful and potentially harmful constituents (PHHCs) (FDA, 2011).

PMI’s focus has been the development of products that do not combust tobacco but which replicate the “smoking experience” as much as possible. Our approach limits pyrolysis and combustion, by heating tobacco at significantly lower temperatures than conventional cigarette (CC). PMI believes that such products present the best opportunity for reducing harm because they produce vastly lower levels of PHHCs and are more likely to be accepted by smokers as substitutes for CCs. Important to this effort has been providing nicotine in a way that closely parallels CC.

The product developed by PMI, and to be assessed in this study, is the Tobacco Heating System 2.2 Menthol (THS 2.2 Menthol). With this product, the heating of the tobacco is maintained below 400°C, a temperature much lower than what is observed for CC, which can reach 900°C. The THS 2.2 Menthol is composed of the ‘THS Tobacco Stick Holder’, dedicated special Menthol Tobacco Sticks made of conventional tobacco, a Charger, and different accessories. The energy of the THS Tobacco Stick Holder is sufficient to maintain approximately a 6 minute session. Unlike CC, the Menthol Tobacco Sticks do not burn down during their consumption and their lengths remain constant after use.

The non-clinical assessment of earlier development of THS 2.2 Menthol described in the investigator’s brochure (PMI, 2013a) supports the initiation of the clinical studies. No new

or increased toxicological hazard in the product's aerosol was detected compared with CC smoke. Further details on the clinical and non-clinical data are provided in the Investigators' Brochure Edition 2 (PMI, 2013a)

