2.2 Purpose of the Study

The overall goal of the study is to provide information on the reduction in the levels of selected BoExp to HPHCs (except for BoExp to nicotine) and to obtain safety information in apparently healthy subjects using the THS 2.2 Menthol as compared to smokers continuing smoking their preferred brand of mCC in confinement setting for 5 days followed by an ambulatory setting of 86 days. Smokers who will be asked to abstain from smoking will be used as a reference point. The smokers in the THS 2.2 Menthol and mCC arms will be allowed to use the product they are allocated to *ad libitum*.

Additional purpose of the study aim is to understand the effect of using THS 2.2 Menthol on selected variables and their potential association to the reduced exposure to HPHCs (e.g. cytochrome P450 1A2 [CYP1A2] and cytochrome P450 2A6 ([CYP2A6] enzymatic activity, pharmacokinetic [PK] profile of nicotine and cotinine, product evaluation, product use and subjective effects related to smoking, human smoking topography, risk markers).

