12.1.5 Significance Level for Inferential Analysis

Unless stated otherwise, all statistical tests will be two-sided and conducted at the 5% level, and all quoted confidence intervals will be two-sided 95% confidence intervals.

The primary endpoints will be tested using a multiple testing procedure to preserve the overall alpha level by simultaneously testing the endpoints using a closed procedure with each test performed at an one-sided alpha level of 2.5%. This implies that statistical significance is required for all primary endpoints in order to be able to make confirmatory claims about any of the endpoints.

Further details will be provided in the SAP.

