#### 5.5 Study Hypotheses And Evaluation Criteria

##### 5.5.1 Hypotheses

The hypothesis to be tested is that the geometric mean level of the BoExp for THS 2.2 Menthol is lower relative to mCC.

For the primary analyses, the hypothesis will be tested on Day 5 for MHBMA, 3-HPMA, S-PMA, and COHb, and on Day 90 Visit for Total NNAL according to the primary and secondary objectives. For the secondary BoExp, the hypothesis will be tested on Day 5, and if significant on Day 90 Visit.

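### The one-sided reduction test and its Day 5 gate are applied to 24-hour urinary nicotine equivalents, where reduction is not the aim, so the formal rule can call only a decrease significant

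*SAP*

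**What the plan says.** **The rule.** SAP 5.5.1 sets one direction: "The hypothesis to be tested is that the geometric mean level of the BoExp for THS 2.2 Menthol is lower relative to mCC". It adds a sequence: "For the secondary BoExp, the hypothesis will be tested on Day 5, and if significant on Day 90 Visit". SAP 12.6.2.1 puts NEQ among the analysed biomarkers ("S-BMA, Total NNAL and NEQ (all analysed from a 24-hour urine collection) at Day 5 and Day 90") and applies the primary ANCOVA. The gate has no exception for nicotine: "For all BoExp, if the results from the Day 5 analysis are significant (one-sided p-value" at or below 0.025), "then the statistical significance will be evaluated for the results of the analysis at Day 90 values". The ratio and 95% CI are promised in the tables and forest plots with no condition attached.

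**The aim.** Protocol 2.2 describes the goal as information on "reduction in the levels of selected BoExp to HPHCs (except for BoExp to nicotine"). Protocol 2.1.2 says of nicotine: "Important to this effort has been providing nicotine in a way that closely parallels CC". In SAP 5.2, the reduction objective (objective 2) does not list NEQ among its endpoints. NEQ sits under objective 4, which is about establishing nicotine levels across confinement and the ambulatory period and states no direction.

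**Classification.** Protocol Table 1 gives nicotine biomarkers their own row, apart from the secondary BoExp. Protocol 7.5.1.3 nevertheless lists NEQ among the selected secondary BoExp.

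**Sidedness.** Protocol 12.1.5: "Unless stated otherwise, all statistical tests will be two-sided and conducted at the 5% level".

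**The concern.** A directional test with a gate suits a marker that the product is meant to lower. For nicotine the product is meant to resemble cigarettes, and the objective asks what the levels are. Applied to NEQ, the rule rewards the one outcome that is not the aim. It also makes the Day 90 significance statement depend on a Day 5 decrease that the product is not designed to produce.

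The companion endpoints of objective 4 are handled differently. SAP 12.6.2.2 compares plasma nicotine and cotinine at every post-baseline timepoint with no gate. Two measures serving one objective would then be reported under different decision rules, and a blank Day 90 p-value for NEQ could be misread as evidence of no difference.

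**Working it through.** **1. Check of the method on the plan's own figure.** SAP Table 20 gives 94% and 98% joint power for a 50% reduction in all five primary BoExp. With SD(log) = √ln(1+CV²), SE = SD·√(1/n_T+1/n_C) and power = Φ[(ln 0.5 − ln MR)/SE − 1.96]:

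- COHb, MR 0.40, CV 0.32, 80:40: SD 0.312, SE 0.0605, power Φ(3.69 − 1.96) = 95.8%.
- Total NNAL, MR 0.30, CV 0.60, 40:40: SD 0.555, SE 0.124, power Φ(4.12 − 1.96) = 98.5%.
- 3-HPMA, MHBMA and S-PMA: each essentially 100%.
- Product: 0.958 × 0.985 = 94.4% (94.3% unrounded), against 94% stated. The second set of assumptions gives 98.2%, against 98%.

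The 50% column is reproduced, so the same formula is used below.

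**2. Inputs for NEQ.** Day 5 numbers 80:40 and Day 90 numbers 40:40 (SAP Table 19). One-sided threshold 0.025 (SAP 12.6.2.1). Null ratio 1, from the hypothesis in SAP 5.5.1. The documents give neither a ratio nor a CV for NEQ, so CVs of 0.3, 0.5 and 0.7 are assumed. These give SD(log) 0.294, 0.472 and 0.631. SE at 80:40 is 0.0568, 0.0915 and 0.1223.

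**3. Probability that the gate opens.** P = Φ(−ln R/SE − 1.96), where R is the true THS:mCC ratio.

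| True ratio R | CV 0.3 | CV 0.5 | CV 0.7 |
|---|---|---|---|
| 0.8 | 98% | 68% | 45% |
| 0.9 | 46% | 21% | 14% |
| 1.0 | 2.5% | 2.5% | 2.5% |
| 1.1 | 0.01% | 0.13% | 0.31% |
| 1.2 | ≤0.03% | ≤0.03% | 0.03% |

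Example, R = 0.8 and CV 0.5: 0.2231/0.0915 = 2.44; Φ(2.44 − 1.96) = 68%. At R = 1 the value is the test's own error rate whatever the CV, so the Day 90 p-value is withheld in 100 − 2.5 = 97.5% of trials, and more often for R above 1. These figures take no gain from baseline adjustment. With a baseline correlation of 0.5, the R = 0.8 row becomes 99.5%, 80% and 56%, and the R = 1 row is unchanged.

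**4. What the reported interval shows.** The SAS code in SAP 12.6.1.1 requests two-sided 95% limits. The probability that the lower limit exceeds 1 is Φ(ln R/SE − 1.96).

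| True ratio R | Day 5, 80:40 (CV 0.3 / 0.5 / 0.7) | Day 90, 40:40 (CV 0.3 / 0.5 / 0.7) |
|---|---|---|
| 1.2 | 89% / 51% / 32% | 79% / 41% / 25% |
| 1.3 | >99% / 82% / 57% | 98% / 70% / 46% |

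To the precision shown, an ungated two-sided 5% test would detect these increases with the same probabilities.

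**5. Which reading of the classification is better supported.** On the side of keeping NEQ apart: Protocol Table 1; the endpoint lists in SAP 5.2; the visit schedules in Protocol Section 9, which name primary, secondary and NEQ as three groups; and Protocol Appendix 1, which does the same with BoExp to nicotine. On the other side: Protocol 7.5.1.3. Protocol 12.6.4 gates secondary BoExp. Read with Table 1 that does not reach NEQ; read with 7.5.1.3 it does.

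**The case against.** The strongest reply is that nothing is lost. A reader might infer that a rise in nicotine exposure could never be found. The documents do not support that: the NEQ ratio and two-sided 95% CI are planned at Day 5 and Day 90, for the PP Set and the FAS (Tables 15.2.3.4 and 15.2.3.5), and an interval wholly above 1 is a two-sided rejection at 5%. This part of the reply stands in full.

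A reader might also infer that Day 90 nicotine exposure would go untested. That is not supported either. SAP 12.6.2.2 compares plasma nicotine and cotinine at each post-baseline timepoint, and SAP 12.6.3.1 compares NEQ in the 4-hour urine fraction at the Day 90 Visit, both without a Day 5 gate. Only the significance call on Day 90 24-hour NEQ is gated.

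A third inference would be that the SAP breaks the protocol's two-sided default. It does not strictly do so: the default yields where something else is stated, SAP 12.6.2.1 states it, and Protocol 7.5.1.3 gives a documented basis for treating NEQ as a secondary BoExp. SAP 12.6.2.2 itself names no sidedness and promises no p-value, so calling the plasma comparison two-sided rests on the protocol default.

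Finally, a ratio near 1 is an expectation. It rests on the design aim and on the predecessor's plasma profile (Protocol 2.1.2), and at 0.8 the gate often opens. What the reply leaves untouched is the mismatch between a directional, gated rule and a non-directional objective, and the conflict between Table 1 and 7.5.1.3.

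**Conclusion.** The point holds as a mismatch between the decision rule and the objective, confined to the p-value. As written, only a decrease in 24-hour NEQ can be called significant. If the true ratio is 1 or higher, the Day 90 p-value is withheld in at least 97.5% of trials; this needs no assumption about the CV. For a true decrease the size depends on the assumed CV: at a ratio of 0.8 the gate opens in 45% (CV 0.7) to 98% (CV 0.3) of trials.

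Severity is minor. NEQ is secondary and outside the success criterion, the estimates and intervals are reported regardless, and the remedy would not change the chance of seeing an increase.

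**What to change.** Take NEQ out of the one-sided test and Day 5 gate in SAP 12.6.2.1. Analyse it with plasma nicotine and cotinine under 12.6.2.2: the same log-scale ANCOVA at Day 5 and Day 90, ungated, reporting the THS:mCC ratio, two-sided 95% CI and two-sided p-value. Align Protocol 7.5.1.3 with Table 1 so that NEQ has one classification throughout.

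The cost is a few lines of wording and a changed p-value column. The data and the model are already planned. Because SAP 12.1.7 makes no multiplicity adjustment for secondary endpoints, no other test is affected.

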12.6.4 Inferential Analysis

For the secondary BoExp and selected risk markers, the hypothesis to be tested is the same as described in Section 12.5.4. This will be tested for secondary BoExp on Day 5, and if significant, on Day 90.

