
Version	Date of Revision	Revision
		
imputation. Clarified that the sensitivity analysis on the compliant population will be produced also for the comparison between THS 2.2 Menthol and SA.
 

○ In Section 12.6.2 and 12.6.2.5:

○ Added summaries for the endpoints of the primary analysis

○ Clarified that the p-value will only be produced at Day 90 conditionally on the statistical significance at Day 5

○ Clarified that the CO breath test will be analyzed in the regular scale

○ Text and list of TFL adjusted according to the general rules for summaries of BoExp

○ Summaries of Nicotine and cotinine concentration not produced as a change from baseline and data will be analyzed on the log space. The mixed model code was removed to analyze results using ANCOVA by timepoint for consistency with other analyses.

○ Clarified that the ratio will be estimated for the analysis of nicotine and cotinine <math>C_{peak}</math> and <math>C_{avg}</math> on Day 5. The median difference will be tabulated for the <math>t_{peak}</math> on Day 5.

○ CYP1A2 and CYP2A6 activity will be analyzed in the log space and the THS 2.2 Menthol:mCC ratio will be presented.

○ Percent change from Baseline will be summarized and listed for the QSU-brief. Data will be analyzed using the same model adopted for the analysis of nicotine and cotinine over study days, amended as appropriate to obtain the required comparison. Only Total score data will be plotted.

○ Summaries and listing of percent change from Baseline added for mCEQ, MNWS, and Ames mutagenicity. Clarified that for the MNWS the results will be presented for the day prior to the assessment.

○ Section of HST questionnaire data moved within the questionnaires Section 7.3.6.

○ Risk markers analyzed for the FAS and PP set. Blood pressure, HbA1c, LDL, HDL, TG, TC, WBC, body weight and waist circumference will be analyzed in the regular scale. 8-epi-PGF2a, 11 DTX-B2, sICAM will be analyzed in the logarithmic scale. Other risk markers will be logarithmically transformed prior to analysis if there is evidence of non-normality by means of Shapiro-Wilks test.

○ In Section 12.6.4:

Philip Morris Products S.A.

Protocol ZRHM-REXA-08-US

Statistical Analysis Plan

Final v 3.0 / 29 May 2015

Confidential

Page 11 of 122

Version	Date of Revision	Revision

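### Exhaled CO is modelled on the raw scale, yet the SAP asks for a THS:mCC ratio with 95% CI and a geometric-mean test, and gives no method for the ratio interval

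*SAP*

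**What the plan says.** Exhaled CO is a listed secondary biomarker of exposure (Protocol Table 1; SAP section 5.2, item 2). Four statements in the plan bear on its analysis.

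- **Model.** SAP section 12.6.2.1: "BoExp will be analyzed using the same model described in Section 12.6.1.1". That section is the primary ANCOVA, coded in PROC GLM with a log outcome and a log baseline.
- **Scale.** The same section then says: "All BoExp apart from CO breath test will be analyzed in the log scale". The revision history (SAP section 3.1, version 2.0) shows that this was deliberate: "Clarified that the CO breath test will be analyzed in the regular scale".
- **Output.** Still in section 12.6.2.1: "LS means for each product along with the ratio (THS 2.2 Menthol : mCC) and 95% CI will be presented in the tables", and "Forest plots of the ratios and 95% CI will also be produced". Neither sentence exempts CO.
- **Hypothesis.** SAP section 5.5.1: "The hypothesis to be tested is that the geometric mean level of the BoExp for THS 2.2 Menthol is lower relative to mCC", and then "For the secondary BoExp, the hypothesis will be tested on Day 5, and if significant on Day 90 Visit". Protocol section 12.6.4 agrees: "For the secondary BoExp and selected risk markers, the hypothesis to be tested is the same as described in Section 12.5.4". Protocol section 12.5.4 is the geometric-mean hypothesis, tested on natural logs.

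SAP section 12.6.2.5 handles mixed scales differently for risk markers. It names which are analysed raw and which on the log scale, and allows a difference or a ratio to be reported.

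**The concern.** The scale, the effect measure and the hypothesis for exhaled CO do not fit together. A geometric mean ratio comes from a log-scale model by back-transforming a difference of log means. Run on raw CO, the referenced code returns arithmetic least squares means and their difference. Exponentiating that difference has no meaning, and the SAP names no other route to a ratio and its interval.

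Whoever programs the tables would have to choose the CO estimand, its interval and its forest-plot entry. SAP section 9 records that the study team was accidentally unblinded, so a choice left open until programming is less protected than usual.

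The raw scale also brings a variance question. If the SD rises with the mean, one pooled residual variance does not suit two arms whose means differ by more than a factor of two.

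**Working it through.** **The plan's own figures.** The SAP gives no mean ratio, CV, standard error or power for exhaled CO, so there is no CO figure to reproduce. Its planning values for the primary endpoints can be checked. Take the log-scale SD as √ln(1+CV²), the effect as ln(MR/0.5), a one-sided 2.5% test and the Table 19 sample sizes. The product of the five powers at a 50% reduction is:

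- YVD-CS01-EU: 0.9582 (COHb) × 0.9999 (3-HPMA) × 1.0000 × 1.0000 × 0.9846 (Total NNAL) = 0.943; stated 94%.
- ZRHX-EX-01: 0.9973 × 1.0000 × 1.0000 × 1.0000 × 0.9846 = 0.982; stated 98%.

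The simple product departs from Table 20 at larger reductions (at 55%: 45% against 38%, and 12% against 6%). Nothing below uses those columns.

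**Inputs.** COHb stands in for CO.

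- Set A: MR 0.40, CV 0.32 (SAP Table 16). Set B: MR 0.44, CV 0.14 (SAP Table 18).
- Day 5: 80:40. Day 90 per-protocol: 40:40. Table 19 gives 40:40 for Total NNAL; I take it to hold for CO because it reflects the expected size of the per-protocol set.
- Assumption: equal CV in both arms. In units of the mCC mean, s_C = CV and s_T = MR × CV.

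**Standard error of the raw difference.**

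- Pooled variance: s_p² = [(n_T−1)s_T² + (n_C−1)s_C²]/(n_T+n_C−2).
- Model SE = √[s_p²(1/n_T+1/n_C)]. True SE = √(s_T²/n_T + s_C²/n_C).
- Set A, 80:40: s_p² = (79×0.016384 + 39×0.1024)/118 = 0.04481. Model SE = √(0.04481×0.0375) = 0.0410. True SE = √(0.016384/80 + 0.1024/40) = 0.0526. The quotient is 0.780, and coverage is 2Φ(1.96×0.780)−1, about 87%.
- Set B, 80:40: s_p² = 0.00902; 0.0184 against 0.0232. The quotient is 0.793, and coverage is about 88%.
- At 40:40 both formulas reduce to √[(s_T²+s_C²)/40], so there is no shortfall. With MR = 1 the two variances are equal, and again there is none.

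**Standard error of a ratio from the same model (delta method).** Model SE of ln ratio = √{s_p²[1/(n_T·MR²)+1/n_C]}. True SE = CV√(1/n_T+1/n_C).

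| | Difference: model / true SE | ln ratio: model / true SE |
|---|---|---|
| Set A, 80:40 | 0.0410 / 0.0526 (22.0% too small) | 0.0680 / 0.0620 (9.7% too large) |
| Set B, 80:40 | 0.0184 / 0.0232 (20.7% too small) | 0.0284 / 0.0271 (4.8% too large) |
| Set A, 40:40 | equal | 0.1038 / 0.0716 (45% too large) |
| Set B, 40:40 | equal | 0.0425 / 0.0313 (36% too large) |

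The shortfall for the difference at 80:40 depends on the ratio: 27.5% at MR 0.2, 18.5% at 0.5, 7.1% at 0.8 and 0% at 1.0.

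**Simulation.** This used 8,000 lognormal data sets per setting, a raw-scale ANCOVA on baseline, and a baseline correlation of 0 or 0.5. At 80:40 the SE of the difference was 20-23% short, with coverage 87.0-88.4%; delta-method ratio intervals covered 95.9-96.8%. At 40:40 (set A) coverage was 94.4-95.1% for the difference and 99.2% for the ratio. With a true ratio of 1 (80:40), coverage of the difference was 95.0-95.3%.

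**Other comparisons.** SAP section 12.6 lets the SA arm enter models where suitable. With the SA mean set to the THS mean divided by 2.10 and the same CV, the Day 5 SE is 30-32% too small for the difference and 4-8% too small for the ratio. For THS versus SA (MR 2.10, CV 0.20, 80:40), the SE of the difference is 24% too large.

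**On the log scale.** One residual variance fits under equal CV. Set A: SE = √ln(1+0.32²) × √0.0375 = 0.0605, so a ratio of 0.40 has a 95% CI of about 0.355 to 0.451. Set B: SE 0.0270, and 0.44 has a CI of about 0.417 to 0.464.

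**The case against.** The raw scale was chosen on purpose, and leaving the log scale is not in itself an error. Protocol section 12.5.4 allows markedly non-lognormal biomarkers to be transformed or analysed non-parametrically. Exhaled CO is one secondary endpoint outside the success criterion (SAP section 5.5.2), and exposure to carbon monoxide is already tested through COHb, on the log scale, as a primary endpoint. All of this stands. It limits the consequence but does not reconcile the scale with the required output.

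A reader might infer that no ratio at all can be had from a raw-scale fit. That goes too far: a ratio of arithmetic means with an interval can be obtained by Fieller's method or the delta method, and a one-sided test of lower mean CO is available. The SAP specifies neither interval method, however, and neither that ratio nor that test addresses geometric means.

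Moving to logs is not the only repair. Reporting a CO difference would also be coherent, and SAP section 12.6.2.5 is a precedent. The documents do not say whether zero readings occur, so a rule for them is a precaution.

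**Conclusion.** The point holds as an internal inconsistency in SAP section 12.6.2.1. For exhaled CO, the specified model does not deliver the ratio, the interval or the geometric-mean test that the plan requires. This rests on the text alone.

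The numerical consequence is conditional on COHb as a proxy, equal CV across arms and a two-arm model. Under those assumptions the raw Day 5 difference has a standard error about 21-22% too small, while a delta-method ratio would have one about 5-10% too large, rising to 36-45% at 40:40.

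Three stronger readings are tempting and are not supported:

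- *The reported ratio has a standard error about 20% too small.* That figure belongs to the difference. In the two-arm model at these planning values, the error for the ratio runs the other way.
- *The raw-scale interval is too narrow in general, so the test is inflated.* There is no shortfall for the difference at the planned Day 90 per-protocol size, and none when the true ratio is 1. Under equal CV the type I error of the test against mCC is therefore not inflated.
- *Smoking topography has the same error.* SAP section 12.6.3.3 does not state a scale. It asks for a ratio and points to code resembling section 12.6.1.3, which is log-scale code. That pointer accompanies log analyses reported as ratios (section 12.6.2.2) and questionnaire scores reported as differences (section 12.6.3.2.2), so it settles nothing. Topography is not a biomarker of exposure, so the geometric-mean hypothesis does not cover it, and no effect size or CV is given for it.

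**What to change.** Preferred: in SAP section 12.6.2.1, remove the exception for CO. Analyse ln(CO) with the same ANCOVA as the other biomarkers, with a log baseline, and report the back-transformed ratio and 95% CI. State a rule for zero or below-limit readings, for example half the smallest recordable value, in line with the LLOQ/2 rule for laboratory parameters in SAP section 12.1.5. This puts CO on the same footing as COHb and leaves the tables, forest plots and hypothesis unchanged.

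Alternative: keep the raw scale, report the difference with an unequal-variance standard error, take CO out of the ratio tables and ratio forest plots, and restate its hypothesis on arithmetic means in SAP section 5.5.1.

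Either is a change of SAP wording with no effect on data collection. The cost of the first is the convention for zero readings. The cost of the second is a separate output and hypothesis for one biomarker. Separately, SAP section 12.6.3.3 could state the topography scale so that it matches the ratio it reports.
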